**Protocol Revision History**

Initial Approval Version	02/23/2018
Amendment #1 Version	08/28/2018
Amendment #2 Version	01/14/2019
.....	.....PRMC Only
Amendment #2 Version	01/24/2019
Amendment #3 Version	08/26/2019
Amendment #4 Version	01/15/2020
Amendment #5 Version	03/31/2020
Amendment #6 Version	11/13/2020

## Glossary of Abbreviations

AE	Adverse event
ALT (SGPT)	Alanine transaminase (serum glutamate pyruvic transaminase)
AST (SGOT)	Aspartate transaminase (serum glutamic oxaloacetic transaminase)
AUC	Area under the curve
CBC	Complete blood count
CFR	Code of Federal Regulations
CMP	Comprehensive metabolic panel
CR	Complete response
CRF	Case report form
CRT	Chemoradiation
CT	Computed tomography
CTCAE	Common Terminology Criteria for Adverse Events
CTEP	Cancer Therapy Evaluation Program
DAI	Dosage and administration instructions
DC	Disease control
DFS	Disease-free survival
DLT	Dose limiting toxicity
DNA	deoxyribonucleic acid
DSM	Data and Safety Monitoring
ECG (or EKG)	Electrocardiogram
ECOG	Eastern Cooperative Oncology Group
EDTA	ethylenediaminetetraacetic acid
FDA	Food and Drug Administration
FDG	Fluorodeoxyglucose
FOE	Fiberoptic endoscopy
HDPE	High-density polyethylene
HIV	Human Immunodeficiency Virus
HNSCC	Head and neck squamous cell carcinoma
HPV	Human papilloma virus
HRPO	Human Research Protection Office (IRB)
HSR	Hypersensitivity reaction
IHC	Immunohistochemistry
IMRT	Intensity-modulated radiation therapy
IND	Investigational New Drug
INR	International normalized ratio
IPM	Investigational Product Manual
IRB	Institutional Review Board
ISH	In situ hybridization
IULN	Institutional upper limit of normal
IV	Intravenous

IVPB	IV piggyback
mDLx	Microlaryngoscopy
MRI	Magnetic resonance imaging
MTD	Maximum tolerated dose
NCCN	National Cancer Center Network
NCI	National Cancer Institute
NEJM	New England Journal of Medicine
NIH	National Institutes of Health
NS	Normal saline
OHRP	Office of Human Research Protections
OPSCC	Oropharyngeal squamous cell carcinoma
OR	Overall response
OS	Overall survival
PD	Progressive disease
PEG	Percutaneous endoscopic gastrostomy
PET	Positron emission tomography
PFS	Progression-free survival
PI	Principal investigator
POACRT	Post-operative adjuvant CRT
PR	Partial response
PS	Performance status
PT	Prothrombin time
PTS	Primary tumor site
PTT	Partial thromboplastin time
QASMC	Quality Assurance and Safety Monitoring Committee
QOL	Quality of life
RECIST	Response Evaluation Criteria in Solid Tumors (Committee)
RM	Recurrent/metastatic
RNA	Ribonucleic acid
RPPA	Reverse phase protein array
RT	Radiation therapy
RTOG	Radiation Therapy Oncology Group
SAE	Serious adverse event
SCC	Siteman Cancer Center
SD	Stable disease
TPP	Time to progression
UPN	Unique patient number

## **1.0 BACKGROUND AND RATIONALE**

### **1.1 Head and Neck Squamous Cell Carcinoma (HNSCC)**

HNSCC is the sixth most common cancer with over 50,000 new cases diagnosed each year in the USA and 600,000 new cases each year worldwide. Most patients present with stage III-IV, non-metastatic disease that is due to smoking and unrelated to the human papillomavirus (HPV). Compared to HPV-related oropharyngeal squamous cell carcinoma (OPSCC), patients with HPV-unrelated HNSCC are older, smoke more, and have a less favorable prognosis.

Acceptable treatment options for these patients include definitive chemoradiation therapy (CRT), surgery followed by post-operative adjuvant CRT (POA[C]RT), or induction chemotherapy followed by CRT. Although there is general agreement that all three approaches result in similar outcomes, in actual practice, most patients are treated with definitive CRT. This pattern reflects the fact that most of these patients are treated in the community setting where definitive CRT is widely practiced, but surgery and induction chemotherapy are not.

### **1.2 Definitive CRT Options and Efficacy Outcomes**

Cisplatin or cetuximab are the two most common agents given concurrently with definitive radiation therapy (RT). Cisplatin is the gold standard systemic therapy recommended to be given concurrently with RT. Either high-dose bolus (100 mg/m^2 cisplatin on Days 1, 22, and 43 of once daily RT or 100 mg/m^2 cisplatin on Days 1 and 22 of accelerated RT) or weekly (40 mg/m^2) cisplatin regimens are recommended in the NCCN practice guidelines. Cetuximab, a taxane, or 5-FU added to cisplatin and RT are no better than cisplatin monotherapy and RT. However, cisplatin results in substantial acute toxicity (mucositis, renal dysfunction, vomiting) and can only be administered safely to patients with normal renal function, good performance status, and low comorbidity index.

Cetuximab and RT has emerged over the last decade as an alternative to cisplatin and RT, based on the results of the Bonner Trial (NEJM) which found that cetuximab and RT was more efficacious than RT alone. Also, cetuximab did not increase the risk of mucositis compared with RT alone and was not associated with renal dysfunction or vomiting.

Although there have been no published head-to-head comparisons of cetuximab and RT vs cisplatin and RT, the absolute magnitude of the improvement in overall survival (OS) (10%) with cetuximab and RT was comparable to historical data with cisplatin and RT. However, controversy exists as to whether the efficacy of cetuximab and RT is as good as cisplatin and RT. Several retrospective reports showed better efficacy outcomes with cisplatin and RT. The ongoing RTOG 1016 trial is comparing the efficacy and tolerance of these two CRT regimens in patients with HPV-related OPSCC. Similar studies are not planned or ongoing in patients with HPV-unrelated HNSCC.

Based on the controversy surrounding the comparability of these two CRT regimens, current practice at most programs is to route HNSCC patients with excellent performance status and adequate vital organ function to receive CRT with high dose bolus cisplatin. However, it is feasible to administer cetuximab but not cisplatin to a broader mix of patients, particularly those with reduced renal function, poor performance status, and a high comorbidity index. As such, cetuximab has been widely selected over cisplatin to be combined with RT for HNSCC patients with reduced performance status and/or vital organ function.

The efficacy of CRT in patients with locally advanced p16INK4a negative/HPV-unrelated HNSCC is surprisingly modest with a substantial risk of disease recurrence and death. RTOG 0129 and RTOG 91-11 provide reference points for efficacy of CRT using cisplatin. In patients with p16INK4a negative OPSCC, RTOG 0129 found that CRT with cisplatin resulted in three-year OS of 57%, progression-free survival (PFS) 43%, local-regional failure rate 52%, and distant metastasis rate of 16%. In patients with larynx SCC, RTOG 91-11 found that CRT with cisplatin resulted in two-year OS of 74%, DFS 61%, local-regional failure rate 20%, and distant metastases rate of 8%. The poorest outcomes occur in the infrequent subset of patients with hypopharynx SCC where the 5-year OS was 38% and the local-regional and distant failure rate was 60%. The Bonner trial provides reference points for the efficacy of CRT using cetuximab. The two-year local-regional failure rate was 50%, the distant metastases rate was 16%, and the median OS varied based on sub-site: 32 months for larynx SCC, 24 months for p16INK4a negative OPSCC, and 13 months for hypopharynx SCC.

In the pool of patients with p16INK4a negative/HPV-unrelated HNSCC, larynx SCC, and hypopharynx SCC, the majority (> 90%) of relapse events occur within 18 months of completion of CRT using either cisplatin or cetuximab.

### 1.3 Biology of p16INK4a negative (HPV-unrelated) HNSCC

HNSCC is a heterogeneous disease. Based on unique gene expression signatures, at least four subgroups have been defined, each with distinct signaling pathways. Despite this heterogeneity, aberrant cell cycle regulation is a ubiquitous event. The mechanism underlying unrestrained proliferation varies depending on the tumor's transcriptionally-active HPV status. In HPV-related HNSCC, E7 viral protein drives unrestrained proliferation by promoting Rb degradation. In HPV-unrelated HNSCC, Rb inactivation occurs through hyper-activation of the Rb inhibitory complex CDK4/cyclin D. CCND1 (encoding cyclin D1, the regulatory subunit of the complex) is amplified and/or the CDK4/6 inhibitor p16INK4a is inactivated in nearly all of these cancers. Alterations of CCND1 and p16INK4a are rare in HPV-related HNSCC. As a result, p16INK4a is overexpressed in HPV-related HNSCC and under expressed in HPV-unrelated HNSCC.

The genetics of HPV-unrelated HNSCC influences the clinical course. CCND1 amplification and p16INK4a inactivation are poor prognostic factors in HNSCC, in part because cyclin D1 overexpression adversely affects tumor response to EGFR inhibitors and cisplatin. In HNSCC cell lines, cyclin D1 amplification and/or overexpression

correlated with resistance to these drugs. Studies in HNSCC reveal that cyclin D1 overexpression is predictive of resistance to cisplatin.

#### **1.4 Selective CDK4/6 Inhibition with Palbociclib**

The essential roles of CDK4/6 and cyclin D1 in driving cell cycle progression from G1 into S phase motivated intense investigation into blocking this regulatory complex. In pre-clinical models, CDK4/6 inhibition inhibits both Rb hyperphosphorylation and cell cycle progression, and the efficacy of inhibition in some models correlated with increased cyclin D1 and decreased p16INK4a expression. Palbociclib is the first approved selective inhibitor of the CDK4/6 kinases. Palbociclib exerts potent anti-proliferative effects on Rb-positive cell lines and human breast and colon xenografts. Palbociclib results in decreased Rb phosphorylation and Ki-67 expression in Rb-positive models but has no activity in Rb-negative tumor xenografts. As such, phase I trials restricted the evaluation of palbociclib to patients with Rb-positive cancers. These studies determined that the dose-limiting toxicity (DLT) of palbociclib was neutropenia and the maximum tolerated dose (MTD) was 125 mg once daily, administered for 21 days of each 28 day cycle. The efficacy of palbociclib was demonstrated in estrogen receptor positive breast cancer and in mantle cell lymphoma, tumors in which cyclin D contributes to their pathogenesis.

**Time-to-best tumor response occurred by Day 56 (end of Cycle 2) in all cases.**

Upon completion of the enrollment on the phase I trial, patients are currently being enrolled on the phase II component of the protocol, in which patients with platin-refractory HNSCC (Cohort 1) or cetuximab-refractory HNSCC (Cohort 2) are treated with palbociclib and cetuximab. Preliminary results of the phase II trial along with the phase I trial results are shown in the Swimmer's Plot below. As can be seen, the median TTP with palbociclib and cetuximab is longer than that of a historical cohort treated with cetuximab monotherapy.

Swimmer's plot showing the TTP for each patient treated with palbociclib and cetuximab. Patients treated on phase I are colored in blue. Patients treated on phase II are divided by cohort: platin-resistant in green and cetuximab-resistant in lavender. Partial tumor responses are noted with a red triangle. The vertical black line is the historical median TTP to cetuximab monotherapy and the vertical red line is the median TTP with palbociclib and cetuximab based on the phase I data.

*This trial, the first to evaluate a CDK4/6 inhibitor in HNSCC, determined that palbociclib 125 mg/day on days 1-21 every 28 days with cetuximab was safe. Tumor responses were observed, even in cetuximab- or platin-resistant disease.*

## 2.0 OBJECTIVES

### 2.1 Primary Objective

Determine the tumor response rate of newly diagnosed p16INK4a negative, HPV-unrelated

HNSCC to neoadjuvant palbociclib monotherapy given over two cycles.

## **2.2 Secondary Objectives**

1. Determine the combined local-regional disease relapse risk and distant metastases risk at 18 months following completion of CRT.
2. Determine the median and two-year PFS and OS (stratified by cohort) of patients treated with the three step sequence of palbociclib monotherapy, CRT, and adjuvant palbociclib monotherapy.

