#### **14.3 Secondary Endpoints**

- Local-regional disease relapse, a binary variable (Yes vs. No). Local-regional disease relapse rate is defined as the proportion of subjects alive who have local-regional progressed disease at 18 months following completion of CRT.
- Distant metastases, a binary variable (Yes vs. No). Distant metastases rate is defined as the proportion of subjects alive who have distant metastases at 18 months following completion of CRT.
- Progression-free survival (PFS), defined as the days from the start of Step 2 (CRT) to the first documentation of disease progression or death from any cause or the end of follow-up.

- Overall survival (OS), defined as the days from the time of diagnosis to death from any cause or the end of follow-up.

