##### **14.6.2 Secondary Endpoints Analyses**

Local-regional disease relapse rate and distant metastases rate and their corresponding 95% confidence intervals will be calculated in each cohort, separately. PFS and OS at two-year will be presented in subject listings. PFS and OS will be analyzed by Kaplan-Meier method in each cohort, separately. Paired t-test or paired-sample Wilcoxon Signed Rank test will be used to compare the genomic, RNA, and protein expression data derived at baseline and then after two cycles of neoadjuvant palbociclib monotherapy. The association between the genomic, RNA, and protein expression data derived after 2 cycles of palbociclib monotherapy and local-regional disease relapse/distant metastases will be explored through independent t-test, Fisher's Exact test, or Kruskal-Wallis test as appropriate.

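### Secondary objective 1 asks for a combined 18-month relapse risk, but the plan has only two separate endpoints, each estimated by cohort

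*Combined protocol and SAP*

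**What the plan says.** The first secondary objective in Section 2.2 reads "Determine the combined local-regional disease relapse risk and distant metastases risk at 18 months following completion of CRT". It mentions no cohorts. The second objective, directly below it, does: "Determine the median and two-year PFS and OS (stratified by cohort) of patients treated with the three step sequence".

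Section 14.3 turns the first objective into two yes/no endpoints. The local-regional rate is the "proportion of subjects alive who have local-regional progressed disease at 18 months following completion of CRT". The distant rate is the "proportion of subjects alive who have distant metastases at 18 months following completion of CRT". No endpoint covers either event.

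Section 14.6.2 gives the analysis: "Local-regional disease relapse rate and distant metastases rate and their corresponding 95% confidence intervals will be calculated in each cohort, separately". Section 5.0 announces pooling of the two cohorts for the primary aim, and Section 14.6.1 specifies the whole sample for the primary endpoint. Neither is said of relapse.

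**The concern.** The objective, the endpoints and the analysis do not describe the same quantity. *Combined* can mean the risk of either type of failure, or the risk over both cohorts together. On the first meaning there is no composite endpoint. On the second there is no planned whole-sample estimate.

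If this is left open, whoever reports the objective must choose after seeing the data what counts as an event, which patients form the denominator, and how deaths before 18 months are treated. The last choice matters because Section 14.3 restricts both rates to subjects alive. Read literally, a patient who relapses and dies before 18 months drops out of the rate that is meant to measure relapse.

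**Working it through.** The plan states no sample size, power or expected rate for this objective, so there is no figure to reproduce. The check has three parts.

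**1. Does any planned output give the combined risk?**

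| Source | Event | Population |
|---|---|---|
| Objective 1 (2.2) | combined local-regional and distant, 18 months after CRT | no cohort split |
| Endpoints (14.3) | local-regional; distant; separately | subjects alive |
| Analysis (14.6.2) | each rate with a 95% CI | each cohort separately |
| PFS (14.3, 14.6.2) | progression or death from any cause | each cohort separately |

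PFS does not fill the gap. It counts deaths without relapse. Its clock starts at Step 2 in Section 14.3 (at start of treatment in Section 13.4.5), not at completion of CRT. Its stated time point is two years.

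**2. Can an either-event risk be derived from the two rates?**

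Let a be the local-regional risk and b the distant risk. Then

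P(either) = a + b − P(both), where P(both) can lie between max(0, a + b − 1) and min(a, b).

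So max(a, b) ≤ P(either) ≤ min(1, a + b). The inputs are the reference rates in Section 1.2, used only for illustration.

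- p16-negative oropharynx, cisplatin CRT, three years: a = 52%, b = 16%. Lower bound 68 − 16 = 52%; upper bound 68 − 0 = 68%. If the two events were independent: 1 − 0.48 × 0.84 = 59.7%.
- Larynx, cisplatin CRT, two years: a = 20%, b = 8%. Lower bound 28 − 8 = 20%; upper bound 28%. If independent: 1 − 0.80 × 0.92 = 26.4%.

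The width left undetermined equals the smaller rate: 16 points in the first case and 8 in the second. In patients, 52% and 16% of the planned 24 are about 12 and 4 events. The composite could then be any number from 12 to 16 patients, that is 50% to 67%.

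**3. Can a pooled-cohort rate be derived?**

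Yes. With x1 events among n1 patients in one cohort and x2 among n2 in the other, the pooled rate is (x1 + x2)/(n1 + n2). Section 14.6 provides for counts as well as percentages. On this meaning the estimate is unplanned, but it can be recovered.

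**The case against.** The strongest reply is that *combined* is loose wording for both risks. The objective uses the word risk twice, which reads like a list of two quantities, and Sections 14.3 and 14.6.2 follow that list. On this reading both quantities are estimated with intervals, and a small edit to Section 2.2 settles the matter. That reading is possible and cannot be excluded. Against it, exploratory objective 2 in Section 2.3 names the same pair without the word, so on this reading the word does no work in objective 1. An edit is needed in any case.

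It is also fair to say that the endpoint is secondary, that Section 14.6 declares all analyses exploratory, and that patient-level data would allow a composite later. This limits the harm. It does not settle the event rule or the handling of deaths in advance.

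Three stronger inferences are tempting, and the documents do not support them.

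- *Adding the rates would overstate the risk by at least 11 points.* Section 1.2 reports "three-year OS of 57%, progression-free survival (PFS) 43%, local-regional failure rate 52%, and distant metastasis rate of 16" per cent. A reader might take the PFS figure as a cap of 100 − 43 = 57% on any failure, against a sum of 68%. This needs the three figures to share one population and one method. The protocol does not say whether the failure rates are cumulative incidences or come from a method that censors deaths. They are also three-year figures, and the plan nowhere proposes adding the rates.
- *The planned results could not be compared with the protocol's benchmarks.* Only the hypopharynx reference is in joint form ("the local-regional and distant failure rate was 60" per cent). The other three give separate local-regional and distant rates, and no formal comparison with any of them is planned.
- *Wide intervals in small cohorts show the defect.* They follow from a total of 24 patients and would affect the composite equally. The cohort sizes are not stated.

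**Conclusion.** The mismatch stands. Objective 1 as worded is not produced by the planned analysis unless *combined* means no more than both risks. The consequence depends on the meaning. An either-event risk is neither planned nor derivable from the two rates, which leave it open by 16 points at 52% and 16%, and by 8 points at 20% and 8%. A pooled rate is unplanned but follows from the cohort counts.

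The ranges rest only on the bounds for two overlapping events. The reference rates are at two and three years in particular sub-sites, so the ranges show the size of the ambiguity and do not forecast the 18-month result.

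This is a worthwhile, inexpensive correction to a secondary objective. It does not affect the primary endpoint.

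**What to change.** In Section 14.3, define any relapse as the first local-regional or distant failure within 18 months of completing CRT, and state that a patient who relapses and later dies counts as an event. State also how a failure found at the 18-month visit is counted, since Section 5.3.6 gives that visit a window of one month either side.

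In Section 14.6.2, estimate the 18-month cumulative incidence of any relapse with a 95% CI, for the whole sample and by cohort, with death without relapse as a competing event. Report the local-regional and distant rates on the same basis as supporting results, so that they no longer depend on an alive-only denominator. Say whether the biomarker comparisons in that section use the composite or each component.

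If only the two separate risks were intended, delete *combined* from objective 1 and state that they are reported by cohort.

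The cost is a few lines of wording and, for the composite, one extra table from data already collected.

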## **2.3 Exploratory Objectives**

1. Explore potential pharmacodynamic determinants of tumor response to palbociclib monotherapy using genomic, RNA, and protein expression methods.
2. Explore potential pharmacodynamic determinants of locoregional disease relapse risk and distant metastases risk to palbociclib-based therapy using genomic, RNA, and protein expression methods.

# **3.0 PATIENT SELECTION**

## **3.1 Inclusion Criteria**

1. Larynx SCC, hypopharynx SCC, or oral cavity SCC. HPV-unrelated OPSCC [defined as p16INK4a negative by IHC (staining in < 70% of cells) or HPV High Risk (Type 16 or 18) negative by ISH]. P16INK4a positive larynx SCC, hypopharynx SCC, and oral cavity SCC are eligible given the unknown effect of this on the biology of SCC of these subsites.
2. Overall Stage III, IVA, or IVB disease per AJCC version 7.0.
3. Measurable disease defined as lesions that can be accurately measured in at least one dimension (longest diameter to be recorded) as  $\geq 10$  mm with CT scan, as  $\geq 20$  mm by chest x-ray, or  $\geq 10$  mm with calipers by clinical exam.
4. At least 18 years of age.
5. Normal bone marrow function as defined below:
  - a. Absolute neutrophil count  $\geq 1,000/\text{mcL}$
  - b. Platelets  $\geq 100,000/\text{mcL}$
  - c. Hemoglobin  $\geq 9.0 \text{ g/dL}$
6. QTc  $< 500$  msec by Fridericia
7. Women of childbearing potential and men must agree to use adequate contraception (hormonal or barrier method of birth control, abstinence) prior to study entry, for the duration of study participation, and for 90 days after completion of treatment. Should

- a woman become pregnant or suspect she is pregnant while participating in this study, she must inform her treating physician immediately.
8. Ability to understand and willingness to sign an IRB approved written informed consent document (or that of legally authorized representative, if applicable).

### **3.1.1 Additional Cohort 1 Eligibility Criteria**

Patients enrolling to Cohort 1 must meet all of the following criteria:

1. ECOG performance status 0-1 (see Appendix A).
2. Adequate organ function defined as:
  - a. Serum creatinine  $\leq 1.5 \times$  IULN and creatinine clearance  $\geq 75$  mL/min
  - b. Bilirubin  $\leq 1.5 \times$  IULN
  - c. ALT and AST  $\leq 2.5 \times$  IULN

